3.3. Endpoints

3.3.1. Co-Primary Endpoint

1. Minimum stent area (MSA) at the site of maximum calcification at the end of the index procedure
2. Target lesion failure (TLF) (cardiovascular death, non-fatal myocardial infarction related to the target vessel, unplanned ischemia-driven target lesion revascularization) at 1 year

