3.3.2. Secondary Endpoints

1. Individual components of TLF at 1 month and 1 year.
2. Minimum stent area (MSA) measured at the end of the index procedure.
3. Strategy success defined as:
 - Successful stent delivery
 - $\geq 80\%$ stent expansion

- Complete stent apposition
- No edge dissection
- Full lesion coverage with <50% plaque burden at proximal and distal references
- TIMI 3 flow
- 4. Target vessel revascularization (TVR)
- 5. Target lesion revascularization (TLR)
- 6. Stent thrombosis
- 7. Stroke
- 8. Cardiovascular death
- 9. Acute kidney injury
- 10. Major bleeding, categorized as class 3-5 according to the Bleeding Academic Research Consortium [BARC]
- 11. Procedure time
- 12. Fluoroscopy time
- 13. Radiation exposure (dose-area-product)
- 14. Cost effectiveness analysis

4. Study Population

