5.1.2. Patient withdrawal

Subjects may withdraw their consent and discontinue participation in the study at any time for any reason or no reason, without jeopardizing their medical care. If a subject withdraws consent it will be documented on the study exit form, and the reason for withdrawal will be requested.

All data obtained until the date of withdrawal will be kept and entered into the efficacy and safety analysis. If the patient explicitly requests complete deletion of the records, they will be made aware that data pertaining to serious adverse events (SAEs) will be retained. This should be documented by the site. Subjects will not be replaced.

Once the subject is withdrawn, further follow-up of the patients shall proceed according to the hospital standard procedures.

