5.1.4. Lost to Follow-up

If the subject cannot be reached for a follow-up visit, at least three telephone contacts (or attempts) should be made prior to recording a missed follow-up visit. The subject however remains in the study until the 1-year follow-up. The subject will only be considered as 'Lost to follow-up' if he/she cannot be reached for the final 1-year follow-up.

NOTE:

- More than three attempts can be made, but three is the minimum required.

- In the event contact with the subject cannot be established, the investigator will immediately contact the referring physician. If the referring physician has not had contact with the subject, information from the subjects identified point of alternative contact will be utilized.

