8.2. Analysis sets

Screened set

All potentially eligible subjects meeting the general inclusion and exclusion criteria, who have signed an informed consent form, have had the index procedure and have been entered into the eCRF will be included in this set. These subjects will be followed up until discharge. This set also includes subjects who complete 12 months of follow up.

Full analysis set (FAS)

This set includes all subjects who have signed an informed consent form, have been entered into the eCRF, have had the index procedure completed and have met all inclusion and exclusion criteria. These subjects will have been assessed using the CYCLOPES calcium modification algorithm and will have been followed up to the end of study (12 months).

Per protocol set (PP)

This set will include all subjects from the FAS who have had no major protocol deviations. As outlined in section 11.3.

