8.3.3. Primary analysis

The study will have co-primary endpoints. The co-primary endpoints are minimum stent area (MSA) at the site of maximum calcification measured at the end of the index procedure and target lesion failure (TLF) defined as the composite of cardiac death, non-fatal myocardial infarction related to the target vessel, and unplanned ischemia-driven target lesion revascularization at one-year post-procedure. MSA is a numerical measurement in millimeters, measured at the independent imaging core laboratory. TLF is a binary endpoint (TLF or no TLF).

The primary analysis will be conducted on the FAS and will estimate the proportion of TLF at 1-year with corresponding exact two-sided 95% CI. Descriptive analyses for MSA will be performed.

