11.3. Protocol Deviations

Investigators are not allowed to deviate from this CIP without prior authorization by the Sponsor except under emergency situations when necessary to preserve the rights, safety or well-being of study subjects.

Deviations and non-compliances will be recorded together with an explanation. Deviations or non-compliances that impact the rights, welfare, or safety of subjects shall be reported as soon as possible to the Sponsor and IEC, as required.

If appropriate, corrective, and preventive actions will be discussed by the Sponsor, investigator, and/or the IEC to determine a suitable course of action.

Deviations include, but are not limited to the following list:

- Failure to receive assigned treatment.
- Failure to obtain informed consent prior to conducting study specific activities.
- Inclusion/exclusion criteria not met.
- Incorrect version of the CIP/PIL used.
- Subject could not be reached for a follow-up visit or follow-up visit was outside window.
- AEs not reported by investigators in the required timeframe as specified in the protocol.
- Source data permanently lost.

Site compliance regarding deviations will be reviewed by the clinical study manager on a regular basis. In addition, all deviations from the protocol will be documented in the final report.

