APPENDIX A - Definitions

DEATH

(Academic Research Consortium-2 [ARC 2] definition) [\[2\]](#)

Type of Death Definition

- Cardiovascular death

Cardiovascular death is defined as death resulting from cardiovascular causes. The following categories may be collected:

1. Death caused by acute MI
2. Death caused by sudden cardiac, including unwitnessed, death
3. Death resulting from heart failure
4. Death caused by stroke
5. Death caused by cardiovascular procedures
6. Death resulting from cardiovascular hemorrhage
7. Death resulting from other cardiovascular cause

- Non cardiovascular Death

Non cardiovascular death is defined as any death that is not thought to be the result of a cardiovascular cause. The following categories may be collected:

1. Death resulting from malignancy
2. Death resulting from pulmonary causes
3. Death caused by infection (includes sepsis)
4. Death resulting from gastrointestinal causes
5. Death resulting from accident/trauma
6. Death caused by other non-cardiovascular organ failure
7. Death resulting from other non-cardiovascular cause

- Undetermined

Undetermined cause of death is defined as a death not attributable to any other category, because of the absence of any relevant source documents. Such deaths will be classified as cardiovascular for end point determination.

DISSECTION

(NHLBI [National Heart, Lung, and Blood Institute] classification)

- Type A** Small radiolucent area within the lumen of the vessel disappearing with the passage of the contrast material.
- Type B** Appearance of contrast medium parallel to the lumen of the vessel disappearing within a few cardiac cycles.
- Type C** Dissection protruding outside the lumen of the vessel persisting after passage of the contrast material.
- Type D** Spiral shaped filling defect with or without delayed run-off of the contrast material in the antegrade flow.
- Type E** Persistent luminal filling defect with delayed run-off of the contrast material in the distal lumen.
- Type F** Filling defect accompanied by total coronary occlusion.

MYOCARDIAL INJURY AND MYOCARDIAL INFARCTION

(Fourth Universal Definition of Myocardial Infarction 2018)

Criteria for acute myocardial infarction (MI)

The term myocardial injury should be used when there is evidence of elevated cardiac troponin values (cTn) with at least 1 value above the 99th percentile upper reference limit (URL). The myocardial injury is considered acute if there is a rise and/or fall of cTn values.

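### The FAS text carries a 12-month follow-up clause with no exception for death, which read literally removes cardiovascular deaths from 1-year TLF; separately, 8.5 contradicts 8.3.1 on imputation and its date rule can place an event before the index procedure

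*Protocol*

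**What the plan says.** **Analysis set.** Section 8.2 first defines the FAS by consent, entry in the eCRF, a completed index procedure and full eligibility. A second sentence adds that these subjects will have been assessed with the algorithm "and will have been followed up to the end of study (12 months"). No exception is made for subjects who die, withdraw or are lost. The Screened set, defined just above, is described as followed to discharge and as also containing those who complete 12 months.

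**Use of the set.** Section 8.3.3: "The primary analysis will be conducted on the FAS and will estimate the proportion of TLF at 1-year", as a binary endpoint with an exact two-sided 95% CI. Section 3.3.1 lists the fatal component first: "Target lesion failure (TLF) (cardiovascular death, non-fatal myocardial infarction related to the target vessel". Secondary endpoint 1 in section 3.3.2 is "Individual components of TLF at 1 month and 1 year", and cardiovascular death is also secondary endpoint 8. Appendix A says of deaths of undetermined cause: "Such deaths will be classified as cardiovascular for end point determination".

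**Incomplete follow-up elsewhere.** Section 5.1.2: "All data obtained until the date of withdrawal will be kept and entered into the efficacy and safety analysis". Section 5.1.4, on a subject who cannot be reached: "The subject however remains in the study until the 1-year follow-up". Section 11.3 lists as a deviation: "Subject could not be reached for a follow-up visit or follow-up visit was outside window".

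**Missing data.** Section 8.3.1 rules out imputing missing values unless the SAP describes it. Section 8.5 states without qualification that missing data will be imputed, but then gives only rules for partial dates: a missing day may be set to 1 and a missing month to January, while a missing year is left missing. No lower bound at the index procedure is given.

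**The concern.** Section 8.3.1 states that no hypothesis is formulated, so there is no threshold to pass or fail. The estimated TLF rate and its interval are the result, and the set on which they are computed matters directly.

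The 12-month clause can be read in two ways. It may describe the follow-up planned for subjects already in the set, or it may be a condition for belonging to it. On the second reading, a patient who dies of a cardiovascular cause in month 3 has a TLF event but is excluded from the set in which TLF is counted. The fatal component is then zero by construction, the TLF rate is biased downward, and section 5.1.2 is contradicted because withdrawn subjects' data would not enter the efficacy analysis. The per-protocol set is drawn from the FAS and inherits the problem.

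The missing-data text is a separate fault. Two protocol sections say opposite things about imputation, and the one concrete rule given can produce impossible event times. At stake are the time-based results: TLF components at 1 month and the Kaplan-Meier curves. No effect on the binary 1-year TLF proportion follows unless events with an impossible date are dropped.

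**Working it through.** The protocol has no figure of its own to reproduce here. It gives a target of 500 patients (section 8.4) and no expected TLF or death rate. All rates below are therefore assumptions, shown over a range.

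**1. FAS clause, membership reading**

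Let T be the true 1-year TLF proportion, C the proportion with cardiovascular death (all of them TLF events) and N the proportion with other death. Removing everyone who dies before 12 months gives

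reported rate = (T − C) / (1 − C − N).

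Withdrawal or loss unrelated to outcome shrinks numerator and denominator alike and cancels. With N = 1%:

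| True TLF | C = 1% | C = 2% | C = 3% |
|---|---|---|---|
| 8% | 7.1% | 6.2% | 5.2% |
| 10% | 9.2% | 8.2% | 7.3% |
| 12% | 11.2% | 10.3% | 9.4% |

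The understatement over this grid runs from 0.8 points (T = 12%, C = 1%) to 2.8 points (T = 8%, C = 3%), so it is close to C itself.

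In counts, for T = 10%, C = 2%, N = 1% and 500 patients:

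- All subjects kept: 50/500 = 10.0%, Clopper-Pearson 95% CI 7.5–13.0.
- Deaths removed: events 50 − 10 = 40; denominator 500 − 10 − 5 = 485; 40/485 = 8.2%, CI 6.0–11.1.
- Cardiovascular death, all kept: 10/500 = 2.0%, CI 0.96–3.65.
- Cardiovascular death, deaths removed: 0/485 = 0%, CI 0–0.8.

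On the descriptive reading the bias from this clause is zero.

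**2. Imputation statements side by side**

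Section 8.3.1 says none, with one exception: what the SAP may describe. Section 8.5 is protocol text, not the SAP, and says the opposite. The exception therefore does not reconcile them. Since 8.5 goes on to give only date rules, a dropped negation or a missing restriction to dates is a likely cause.

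**3. Partial-date rule**

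Example: index procedure on 15 June, event on 20 June, day not recorded. The rule gives 1 June, which is 14 days before treatment. If the month is missing too, it gives 1 January.

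To see how often this happens per event with a partial date, I enumerated 365 index dates (one calendar year, each equally likely) against every event day in a window (each equally likely). Both uniform distributions are assumptions.

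| Missing | True event day | Dated before index | Moved to day 30 or earlier |
|---|---|---|---|
| Day | 0–30 | 47.5% | – |
| Day | 31–60 | 0% | 49.1% |
| Day | 0–365 | 4.0% | – |
| Day and month | 0–30 | 95.6% | – |
| Day and month | 0–365 | 49.7% | – |

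The last figure depends on the enrolment pattern: if the 18 months of enrolment in section 3.2 begin on 1 January, a simulation gives about 58%. With only the day missing, the damage is concentrated in the first two months, which is where the 1-month endpoint is decided.

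**The case against.** The case for the descriptive reading is strong. The sentence in 8.2 that defines membership contains no follow-up condition. The disputed words come in a second sentence about subjects already included. The Screened set is built the same way, and nobody would take its statement about follow-up to discharge as excluding an in-hospital death. Sections 5.1.2, 5.1.4 and 11.3 all treat incomplete follow-up as something that happens within the analysed population. A reading that empties a component of the co-primary endpoint is hard to credit as intended. The size given above needs both the less natural reading and assumed rates.

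This shows that the descriptive reading is the likelier intention, but it does not settle the text. Length of follow-up is one of the few features that separate the Screened set from the FAS. Section 5.1.2 covers withdrawals only, and no section says that a patient who dies before 12 months stays in the FAS.

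On dates, the rule is permissive in wording, the number of events with partial dates is unknown and may be small, adverse event records must carry an onset date (section 6.1), endpoint events are adjudicated, and only 4.0% of missing-day events over the full year are placed before the index procedure. A lower bound could also be left to the SAP. All of that limits the effect. But the protocol did not leave the matter open: it stated a rule, and the rule as stated gives wrong times for early events.

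The clash between 8.3.1 and 8.5 stands, although it may be a slip and no non-date imputation method is given.

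**Conclusion.** The concern holds as a conditional one on the FAS and as a plain one on section 8.5. The 12-month clause should not remain in the definition of the set used for a co-primary endpoint. If it is only descriptive it does no harm. If it is applied as written, 1-year TLF is understated by roughly the cardiovascular-death rate, about 0.8 to 2.8 percentage points for true TLF of 8–12%, cardiovascular death of 1–3% and other death of 1%, and cardiovascular death is reported as zero. Those rates are assumptions.

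Sections 8.3.1 and 8.5 contradict each other as they stand. The date rule can put events before treatment or move them into the first 30 days. This bears on the 1-month components and the Kaplan-Meier curves, and the number of events concerned is unknown and may be small. It should be corrected before data freeze, so that the choice of analysis set is not made with the results in view.

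**What to change.** 1. In section 8.2, delete the 12-month clause. Define the FAS as all consented, eligible subjects entered in the eCRF with a completed index procedure, regardless of length of follow-up. State that every death, and every event before withdrawal or loss, is counted.
2. In section 8.5, restrict imputation to partial dates so that it agrees with 8.3.1, and add that no imputed event date may be earlier than the index procedure.

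The planned exact proportion stays the primary estimate. How subjects who leave without an event are counted can remain with the SAP. The cost is a change of wording in two sections. The reported TLF rate may be less favourable than it would be in a completers-only set.

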8.3. Statistical analyses

8.3.1. General considerations

The study design aim is to validate a comprehensive, IVUS guided calcium modification algorithm for moderate to severely calcified coronary lesions and its effects on the primary and secondary outcomes outlined in section 3.3 herein. As such, no statistical hypothesis has been formulated

Proprietary and Confidential - Property of CVRI Dublin, Ireland

in accordance with the single arm, observational design. Descriptive statistics and graphical displays will be used to summarize the study findings and outcomes.

Continuous variables will be summarized by the number of observations, arithmetic mean, standard deviation (SD), median, minimum, maximum and interquartile range unless otherwise stated. For categorial variables, frequency tables will be produced including counts and percentages. Time to event variables will be assessed using Kaplan-Meier curves. There will be no imputation of missing values, unless otherwise described in the statistical analysis plan.

Estimates will be provided with corresponding two-sided 95% Confidence Intervals. No adjustments will be made for multiple testing.

Continuous variables will be reported as mean and standard deviation or median and interquartile range, as appropriate. The distribution of continuous variables will be assessed by the Shapiro-Wilk test. Categorical variables will be reported as counts and percentages and compared by Pearson χ^2 or Fisher exact test, as appropriate. In general, the denominator for the percentage calculation will be based upon the number of non-missing values available, unless otherwise specified.

For time-to-event analysis other than the primary endpoint for the de-novo patients, Kaplan-Meier survival curves as well as confidence intervals based on the log-log transformation will be reported.

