8.3.4. Secondary analysis

All secondary endpoints will be summarized by timepoint (see section 7.3 for details) using appropriate descriptive statistics as detailed above. 95% two-sided confidence intervals will also be calculated for the frequency and mean estimates at each timepoint, as appropriate. Time to event endpoints will be assessed using Kaplan-Meier curves.

Specific details of the analysis of each secondary endpoint, including the rules for handling missing values, will be provided in the SAP.

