8.4. Sample size

Target recruitment of 500 patients.

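### Kaplan-Meier with log-log limits for secondary time-to-event endpoints slightly overstates event proportions and gives no Kaplan-Meier interval while no event has occurred

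*Protocol*

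**What the plan says.** Section 8.3.1 of the protocol sets the general rule. It opens "For time-to-event analysis other than the primary endpoint for the de-novo patients" and continues that "Kaplan-Meier survival curves as well as confidence intervals based on the log-log transformation will be reported". It also states that "Estimates will be provided with corresponding two-sided 95% Confidence Intervals".

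Section 8.3.4, on secondary endpoints, says "Time to event endpoints will be assessed using Kaplan-Meier curves". It adds that "95% two-sided confidence intervals will also be calculated for the frequency and mean estimates at each timepoint, as appropriate", and then defers: "Specific details of the analysis of each secondary endpoint, including the rules for handling missing values, will be provided in the SAP".

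Neither section names a competing-risk estimator, says how a death without the event is handled, or lists which secondary endpoints count as time-to-event. The candidates in section 3.3.2 are the components of target lesion failure (TLF) at 1 month and 1 year, target vessel and target lesion revascularization (TVR, TLR), stent thrombosis, stroke, cardiovascular death and major bleeding.

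The co-primary TLF analysis in section 8.3.3 is separate. It "will estimate the proportion of TLF at 1-year with corresponding exact two-sided 95% CI".

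**The concern.** A patient who dies of another cause can no longer have a repeat revascularization, a stroke or a stent thrombosis. Kaplan-Meier for such an endpoint ordinarily censors that patient at death, as if the event could still happen later. One minus the curve then estimates a risk in a population where nobody dies of anything else, and this is never lower than the proportion of treated patients who have the event. Cardiovascular death has the same problem, with non-cardiovascular death as the competing cause.

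The log-log interval has a separate limitation. It is built on log(-log S), which does not exist at S = 1. Until the first event there are no Kaplan-Meier limits, or the software substitutes its own default. This matters most for the rarest safety endpoints, for 1-month results and for the subgroups of section 8.3.6.

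The study has one arm and no hypothesis test, so absolute event rates and their intervals are its result. There is also a question of consistency. TLF is reported as a proportion, and a patient who dies of a non-cardiovascular cause without TLF, if kept in the denominator, counts as free of TLF. Kaplan-Meier for the TLF components would censor the same patient, which puts the composite and its parts on different risk scales.

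**Working it through.** **Inputs.** The planned size is 500 (section 8.4: "Target recruitment of 500 patients"), follow-up is 12 months and intervals are two-sided 95%. The protocol gives no event rate, death rate or precision target, so there is no stated figure to reproduce. All event and death rates below are assumptions, shown as a range.

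**1. Size of the overstatement.** Let p be the 1-year value of one minus Kaplan-Meier with deaths censored, and d the 1-year risk of competing death. With constant hazards, l = -ln(1-p) and m = -ln(1-d), and

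cumulative incidence = l/(l+m) × [1 - exp(-(l+m))].

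For p = 5% and d = 5%, l = m = 0.0513. The cumulative incidence is 0.5 × (1 - 0.95 × 0.95) = 0.5 × 0.0975 = 4.88%, so the excess is 0.13 points. Other cases:

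| 1 - KM | Death | Cumulative incidence | Excess (points) |
|---|---|---|---|
| 1% | 3% | 0.985% | 0.02 |
| 1% | 5% | 0.975% | 0.03 |
| 1% | 10% | 0.949% | 0.05 |
| 5% | 3% | 4.93% | 0.08 |
| 5% | 5% | 4.88% | 0.13 |
| 5% | 10% | 4.75% | 0.25 |
| 10% | 10% | 9.50% | 0.50 |

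The relative excess is about d/2: 1.5%, 2.6% and 5.3% for d of 3%, 5% and 10%. If every death preceded every event, the excess would reach its upper bound of p × d, for example 5% × 10% = 0.5 points.

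A simulation (500 patients, 4,000 replicates per scenario) agrees with the formula:
- event 5%, death 3%: 0.07 points
- event 5%, death 5%: 0.13 points
- event 10%, death 5%: 0.25 points
- event 10%, death 10%: 0.50 points

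**2. Comparison with sampling error.** The exact 95% interval for 25/500 is 3.26% to 7.29%, about 2 points either side of 5%. The excess at that event rate is 0.08 to 0.25 points.

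**3. Zero events.** At S = 1, log(-log S) is minus infinity and its standard error is 0/0, so no limits exist. With one event in 500 they do exist: 0.03% to 1.41%. The exact upper limit with no events is 1 - 0.025^(1/n), which is 0.74% for n = 500.

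**4. How often this would occur.** The chance of no event in n patients at true risk r is (1-r)^n. For n = 500:

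| True risk | Chance of no event |
|---|---|
| 0.1% | 61% |
| 0.2% | 37% |
| 0.5% | 8% |
| 1% | 0.7% |

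For a subgroup of 150 (an assumed size; the protocol gives none) the chance is 74% at 0.2% and 47% at 0.5%, and the exact upper limit is 2.4%.

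**The case against.** The strongest reply is that this belongs to the SAP. Section 8.1 calls the chapter a summary, and section 8.3.4 leaves endpoint-level detail to the SAP, which is not at hand. The protocol never says that deaths are censored; that is inferred from the ordinary meaning of Kaplan-Meier. This reply stands in part: the SAP may settle how deaths are handled. But the protocol itself names both the estimator and the interval, so the choice can fairly be commented on.

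A reader might infer that a zero-event endpoint would be reported with no interval at all. The text does not support that. Section 8.3.4 also promises intervals for frequencies at each timepoint, so only the Kaplan-Meier interval is lost. What remains is that the method for the frequency interval is not named. A Wald interval at zero events has zero width, and an exact method is stated only for TLF.

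A reader might also infer that every secondary clinical endpoint is affected. The protocol does not say which are time-to-event, and a simple proportion does not carry the censoring bias. The scope of the 8.3.1 sentence is itself unclear, because it refers to de-novo patients, a group the protocol does not define.

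Finally, the effect is small. Section 4.2.2 excludes patients expected to live less than a year, which limits competing mortality, and the bias is well inside sampling error. That is correct, and it is why the point is minor.

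**Conclusion.** The point holds as a minor improvement. Where a secondary endpoint is analysed by Kaplan-Meier with deaths censored, the reported risk is biased upward by about 0.02 to 0.25 points for event rates of 1 to 5% and death rates of 3 to 10%. These rates and the constant hazards are assumptions. The log-log Kaplan-Meier interval does not exist while no event has occurred. By 1 year in the full cohort this is realistic only for true risks of about 0.5% or less; at 1 month and in subgroups it is more likely.

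It would be wrong to conclude that the safety results would be materially misleading, or that the co-primary result is affected. The bias would not change how a descriptive study of 500 patients is read, and TLF already has a proportion with an exact interval.

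**What to change.** In sections 8.3.1 and 8.3.4, and in the SAP:

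- For each secondary endpoint analysed as time-to-event, report the Aalen-Johansen cumulative incidence at 1 month and 1 year.
- Treat as competing only deaths that do not themselves count as the endpoint event under Appendix A and adjudication by the clinical events committee (CEC). A blanket rule that all deaths compete would misclassify some events: the Appendix A definition of TVR takes in death attributed to the target vessel, and stent thrombosis can be confirmed at autopsy. For cardiovascular death, the competing event is non-cardiovascular death.
- Where no event has occurred, report the Clopper-Pearson interval, in line with the exact method already chosen for TLF in section 8.3.3.

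No provision for all-cause death is needed, since it is not a listed endpoint. While the 8.3.1 sentence is being edited, its reference to de-novo patients should be defined or removed.

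The cost is a few words and a standard software option. No new data are needed, because the CEC already adjudicates deaths and Appendix A already separates cardiovascular from non-cardiovascular causes.
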